STUDY DESIGN	Subjects will be screened for the study and complete a 30-day, stable therapy, run-in period with a long-acting beta agonist (LABA) (salmeterol 50 mcg twice daily) and an inhaled corticosteroid (ICS) (fluticasone starting dose at investigator discretion). After the 30-day run-in is complete, at the Baseline Visit (Day 0), subjects will be randomly assigned (1:1) to AVTX-002 or placebo. Fourteen days after randomization, subjects in each treatment group will discontinue salmeterol therapy at Visit 4 (Day 14). After an additional 14 days, at Visit 5 (Day 28), all subjects will taper fluticasone dose to 50%. At Visit 6 (Day 42), all subjects will discontinue the use of fluticasone therapy completely. AVTX-002 or placebo will be administered at Visit 2 (Day 0), Visit 5 (Day 28) and Visit 7 (Day 56). AVTX-002 will be administered at a dose of 600 mg. The final visit will be on Day 98.
PLANNED NUMBER OF SUBJECTS	Approximately 80 completed subjects
PLANNED NUMBER OF STUDY SITES	Approximately 25 sites from the United States will participate
STUDY ENTRY CRITERIA	
Inclusion criteria:
 

Subject is <math>\geq 18</math> years of age at the time of informed consent.

Documented non-eosinophilic asthma diagnosis (<300 eosinophils/<math>\mu</math>L).

Symptoms consistent with a diagnosis of asthma that is poorly controlled as determined by an ACQ score <math>\geq 1.5</math>.

Poorly controlled asthma despite the use of a LABA and ICS for at least 3 consecutive months immediately prior to screening.

Subjects must have had at least one asthma exacerbation in the last 24 months prior to Screening. An asthma exacerbation is defined as follows:

a course of oral corticosteroids because of worsening asthma symptoms, and/or

at least a doubling of the subject's inhaled corticosteroids for at least 14 days because of worsening asthma symptoms.

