### **11 ADVERSE EVENTS**

#### **11.1 Definition of Adverse Events, Period of Observation, Recording of Adverse Events**

##### **11.1.1 Adverse Event Collection**

An AE is defined as any untoward medical occurrence in a patient or clinical investigation subject administered a pharmaceutical product that does not necessarily have a causal relationship with the product. An AE can therefore be any unfavorable and unintended sign (including a new, clinically important abnormal laboratory finding), symptom, or disease, temporally associated with the product, whether related to the product. An AE will be considered treatment-emergent if it occurs after the first dose of investigational product and within 28 days of a subject's last dose of investigational product. Additionally, an AE that occurred prior to dosing with study medication and increased in severity after start of dosing and within 28 days of a subject's last dose of investigational product will also be considered treatment emergent.

All AEs are collected from the time of the informed consent is signed until the end of study (Day 98/ET). This includes events occurring regardless of whether investigational product is administered. Note: Clinically significant observations noted during screening procedures (labs, physical examination, vital signs, etc.) should be entered as medical history. Only if the clinically

significant observation is clearly related to the performance of a screening procedure should it be entered as an AE (e.g., a hematoma because of drawing blood for screening labs). Where possible, a diagnosis rather than a list of symptoms should be recorded. If a diagnosis has not been made, then each symptom should be listed individually.

All AEs must be followed to closure, regardless of whether the subject is still participating in the study. Closure indicates that an outcome is reached or stabilization achieved (i.e. the investigator does not expect any further improvement or worsening of the event). When appropriate, medical tests and examinations are performed so that resolution of an event(s) can be documented.

Events that meet the protocol definition of an asthma related event are captured as part of the primary efficacy endpoint for the study, and therefore need not be recorded as an AE unless they meet the definition of an SAE. Asthma exacerbations that do not meet the protocol definition of an asthma related event should be captured as AEs.

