8 CHANGES IN CONDUCT OR PLANNED ANALYSES FROM THE PROTOCOL

The following changes from protocol conventions are applied:

1.

According to the Schedule of Assessments (Table 1 in study protocol), numbering of assessment day starts at Day 0 at Visit 2, Baseline; ie:

Procedure	Screening	...	Baseline		Doubleblind Treatment Period					
Visit	V 1	...	V 2	V 3	V 4	V 5	V 6	V 7	V 8	V 9/ET
Assessment Week	-4	...	0	1	2	4	6	8	12	14
Assessment Day	Appr -37	...	0	7	14	28	42	No later than 56	84	98

Appr = approximately; ET = early termination; V = Visit

For the purpose of presentation of the study results however, the first day of dosing will be denoted Day 1 (ie, there will be no Day 0). This results in the following changes to numbering of assessment day, according to which the study results will be reported:

Procedure	Screening	...	Baseline		Doubleblind Treatment Period					
Visit	V 1	...	V 2	V 3	V 4	V 5	V 6	V 7	V 8	V 9/ET
Assessment Week	-4	...	0	1	2	4	6	8	12	14
Assessment Day	Appr -37	...	1	8	15	29	43	No later than 57	85	99

Appr = approximately; ET = early termination; V = Visit

2.

According to protocol Section 11.1.1, an AE will be considered treatmentemergent if it occurs after the first dose of investigational product and within 28 days after a subject's last dose of investigational product. However, since the start time for AEs are collected in this study only if AE duration is < 24 hours, the definition for an AE to be considered treatmentemergent will be as follows:

- If AE start time is recorded: an AE will be considered treatmentemergent if it occurs on or after the time of first dose of investigational product and within 28 days after a subject's last dose of investigational product.
- If AE start time is not recorded: an AE will be considered treatmentemergent if it occurs on or after the date of first dose of investigational product and within 28 days after a subject's last dose of investigational product.

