10.7.1 Adverse Events

All AEs are collected from the time that the informed consent is signed until the end of study.

The definition for an AE to be considered treatmentemergent is as follows:

- If AE start time is recorded: an AE will be considered treatmentemergent if it occurs on or after the time of first dose of investigational product and within 28 days after a subject's last dose of investigational product.
- If AE start time is not recorded: an AE will be considered treatmentemergent if it occurs on or after the date of first dose of investigational product and within 28 days after a subject's last dose of investigational product.

Additionally, an AE that occurred prior to the date of first study drug dosing and increased in severity after start of first dosing and within 28 days of a subject's last dose of investigational product will also be considered treatment-emergent. An AE that occurred prior to first study drug dose and then again after first study drug dose at the same severity is NOT considered treatment-emergent.

AE verbatim terms will be coded to a SOC and PT using MedDRA, version 24, 01 Sep 2021.

For incidence of AEs by treatment group, SOC and PT, a subject will be counted only once per SOC and PT.

For AE incidence presented as the number and percentage of subjects with a specific AE, if there is more than one occurrence of an event, the event with the worst severity or the highest rated causality category will be summarized.

Summaries of AEs by SOC and PT will be sorted alphabetically for SOC, then by descending order of frequency of PT (for AVTX-002) within each SOC (then alphabetically for ties).

Summaries of AEs by PT will be sorted by descending order of frequency of PT (for AVTX-002), then alphabetically for ties.

Missing assessments of seriousness, intensity and relationship to study drug that have been queried and remain missing, will be treated 'worst case' for presentation filtering purposes as follows:

- Missing seriousness assessment: AE will be regarded as serious.
- Missing relationship to study drug: AE will be regarded probably related to study drug, except when start date is prior to first dose of study drug (in which case the AE will be regarded not related to study drug).
- Missing intensity assessment:
 - If subject has died, AE will be regarded Grade 5 intensity.
 - If subject has not died but subject had intervention indicated for the AE, AE will be regarded Grade 4 intensity.

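### SAP 10.7.1 excludes same-severity recurrences from the TEAEs, against the protocol definition and without declaring the change

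*SAP*

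**What the plan says.** **Protocol 11.1.1** gives the onset rule, "An AE will be considered treatment-emergent if it occurs after the first dose of investigational product", with an upper limit of 28 days after the last dose. It then adds a second group: "an AE that occurred prior to dosing with study medication and increased in severity after start of dosing", with the same 28-day limit. Protocol 12.3.4.1 repeats the onset rule. Neither section removes a post-dose event because a similar one occurred earlier.

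**SAP Section 8, item 2**, declares a change to this definition and gives one reason: "since the start time for AEs are collected in this study only if AE duration is < 24 hours". Where no start time is recorded, "an AE will be considered treatmentemergent if it occurs on or after the date of first dose of investigational product", again up to 28 days after the last dose. No other departure from the protocol's TEAE definition is listed.

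**SAP 10.7.1** repeats those two bullets and the worsening rule. It then adds that an event seen before dosing and "then again after first study drug dose at the same severity is NOT considered" a TEAE.

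**Collection period.** Protocol 11.1.1 states: "All AEs are collected from the time of the informed consent is signed until the end of study". Before randomization, subjects "complete a 30-day, stable therapy, run-in period". Protocol Table 1 places screening and run-in at roughly Day -37 to Day -30 onward.

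**The concern.** The last sentence of the SAP definition takes out events that every other statement of the definition puts in. A subject with a pre-dose episode on record can have a genuinely new episode after dosing that never reaches the TEAE tables, provided the grade is unchanged.

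Safety and tolerability is a secondary objective, and TEAEs are the adverse event variable on which it is assessed. The flag feeds the SOC and PT tables for all TEAEs, for related TEAEs, for TEAEs leading to discontinuation, for serious TEAEs and for maximum grade. The exclusion applies whatever causality the investigator assigned.

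One consequence is particular to this design. Protocol 11.1.1 asks for asthma exacerbations that do not meet the asthma related event definition to be recorded as AEs. If such an exacerbation occurs in the run-in and recurs at the same grade after background therapy is withdrawn, it enters neither the primary endpoint nor the TEAE tables.

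**Working it through.** The documents state no adverse event rate, so there is no figure to reproduce. The check compares the rules on test cases.

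**Step 1. Apply each rule.** The subject has a Grade 1 headache in the run-in, which resolves. A new headache starts after first dose.

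| New headache | Protocol 11.1.1 and 12.3.4.1 | SAP Section 8 item 2 and 10.7.1 bullets | SAP 10.7.1 with its last sentence |
|---|---|---|---|
| Day 10, Grade 1 | TEAE | TEAE | Not a TEAE |
| Day 10, Grade 2 | TEAE | TEAE | TEAE |
| More than 28 days after last dose | Not a TEAE | Not a TEAE | Not a TEAE |

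The rules part only in the first row. If the run-in headache had been Grade 2 and the new one Grade 1, the last sentence would not apply and the bullets would make it a TEAE. A milder recurrence would count while an equal one would not.

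**Step 2. Direction.** The sentence only removes events. Each TEAE count under the SAP is therefore at or below the count under the protocol rule.

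**Step 3. Is it programmable as written?** The SAP does not say whether the two episodes are matched on verbatim term or on preferred term. Two programmers could produce different counts.

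**Step 4. Scale, by assumption only.** From the documents: a pre-dose window of 30 to 37 days; a post-dose window of about 84 days (third dose by Day 56, plus 28); 40 subjects per arm. Assumed: 28-day incidence of one term, m, from 5% to 20%; probability s from 0.5 to 0.9 that a recurrence has the same grade; no other qualifying post-dose episode in a removed subject.

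Share of subjects with the TEAE who are removed = s × P(episode before and after dosing) / P(episode after dosing).

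- *Episodes independent within subject*, m = 10%, 37 days, s = 0.9. The daily hazard is -ln(0.9)/28 = 0.00376. P(before) = 1 - exp(-37 × 0.00376) = 0.130. P(after) = 1 - 0.9³ = 0.271, or 10.8 of 40. Share removed = 0.9 × 0.130 = 12%, leaving 9.6 of 40.
- *Subjects differ in underlying rate* (gamma frailty, shape 0.5), same inputs: 9.4 of 40 becomes 7.0 of 40, a loss of 25%.
- Over the whole assumed grid, the loss is 3% to 23% under independence and 5% to 40% with frailty (shape 1 or 0.5).

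These figures show how the effect depends on recurrence. They do not estimate it for this trial.

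**The case against.** The best defence is that the sentence directly follows the worsening rule and is meant as its complement: a pre-dose condition counts if it worsens and does not if it is unchanged. The headache example in Protocol 11.1.1, where an intermittent pre-dose complaint is recorded anew once its intensity rises, fits that reading. A general rule followed by an explicit exception is also not, in itself, a logical contradiction within one section. This would hold for one continuing or intermittent AE record. It does not fit the SAP's wording, which describes an event that happened before dosing and then happened again, and so covers separate new episodes. Nor does it explain why Section 8 sets out the revised definition without the exception.

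Other points on that side do stand:

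- **Events are not lost.** The listing of all AEs and the any-AE row keep them. Serious AEs get their own table if they differ from serious TEAEs, and the listings for death and discontinuation are not limited to TEAEs. However, the any-AE row mixes pre- and post-dose events, and a non-serious excluded event appears in no SOC and PT table.
- **The pool of pre-dose AEs is limited.** Clinically significant screening observations go to medical history unless a screening procedure clearly caused them.
- **Both arms are treated alike**, and the safety analysis is descriptive.

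A reader might infer that a drug raising the frequency of a mild event would show nothing. The documents do not support that: subjects with no pre-dose episode are untouched, so an increase is diluted but still visible. A reader might also infer that the commonest events are the ones undercounted. That is plausible but unsupported, since no rates are given.

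**Conclusion.** The point holds as a discrepancy of definition. For a separate post-dose episode at the same severity as a pre-dose one, the SAP's last sentence gives the opposite answer to Protocol 11.1.1 and 12.3.4.1, to SAP Section 8 item 2 and to the bullets just above it, and the departure is not declared. Only the direction is certain: TEAE counts fall or stay the same, and a true increase in recurrent same-grade events can be attenuated. The amount rests on recurrence rates that the documents do not give. The primary efficacy analysis is unaffected. This is a minor point with a cheap remedy.

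It would go too far to read Protocol 11.1.1 as making every new post-dose onset a TEAE. AEs are collected to Day 98, while the third dose is due by Day 56 and its 28-day limit ends by Day 84. For a subject dosed on Day 56, the last 14 days (98 - 84) lie outside the window under either definition.

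**What to change.** Delete the last sentence of the TEAE definition in SAP 10.7.1. Alternatively, limit it to a single AE that was ongoing at first dose and did not worsen. Either way, any new onset on or after first dose and within 28 days of last dose is then a TEAE. The 28-day limit must stay. The start on or after first dose is the SAP's own declared convention in Section 8; the protocol says after first dose.

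If the exclusion is intended, list it in Section 8 with its reason. State how a pre-dose and a post-dose episode are matched (verbatim or preferred term) and what happens when the recurrence is milder.

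The cost is one SAP sentence and, if it is deleted, a simpler TEAE flag. TEAE counts would be slightly higher in both arms. No new data are needed.

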## 11.2 Severity of Adverse Events

The medical assessment of clinical severity of an AE will be determined using the definitions outlined in Common Terminology Criteria for Adverse Events (CTCAE), Version 5.0 (Published November 27, 2017, by the US Department of Health and Human Services, National Institutes of Health, National Cancer Institute):

Grade 1 Mild; asymptomatic or mild symptoms; or clinical or diagnostic observations only; or intervention not indicated

Grade 2 Moderate; or minimal, local or non-invasive intervention indicated; or limiting age-appropriate instrumental activities of daily living (ADL)

Grade 3 Severe or medically significant but not immediately life-threatening; or hospitalization or prolongation of hospitalization indicated; or disabling; or limiting self-care ADL

Grade 4 Life-threatening consequences; or urgent intervention indicated

Grade 5 Death related to AE

The above grading guidelines should be used whenever possible. For AEs that cannot be graded using CTCAE, the severity should be graded using mild (Grade 1), moderate (Grade 2), severe (Grade 3), life threatening (Grade 4), and fatal (Grade 5).

Please refer to the above-referenced CTCAE document for full description of CTCAE terms and instrumental and self-care ADLs. It is important to distinguish between severe AEs and SAEs. Severity is a classification of intensity whereas an SAE is an AE that meets serious criteria, as

described in Section 11.2.2.3.

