### 11.2.3 Fatal Outcome

Fatal should only be selected as an outcome when the AE results in death. If more than 1 AE is possibly related to the subject's death, the outcome of death should be indicated for each such AE.

Any AE that results in the subject's death must have fatal checked as an outcome with the date of death recorded as the resolution date. AEs resulting in death must be reported within 24 hours as a SAE, if not already reported as such. In the event of a subject's death, data should be collected on whether the death occurred after the withdrawal of care and, if so, the reason for the withdrawal of care.

For other AEs, ongoing at the time of death that did not contribute to the subject's death, the outcome should be considered not resolved, without a resolution date recorded.

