 - If none of the previous conditions are met, AE will be regarded Grade 3 intensity.

The following subject listings will be provided, using the SAS:

- All AEs (including TEAEs and nonTEAEs)
- All serious AEs (including serious TEAEs and serious nonTEAEs)
- All AEs leading to death
- All AEs leading to discontinuation of study drug

An overall summary of AEs will be provided, containing the number and percentage of subjects by treatment group with:

- any AEs
- any serious AEs
- any TEAEs
- any study drug related TEAEs

- any TEAEs leading to study drug discontinuation
- any study drug related TEAEs leading to study drug discontinuation
- any TEAEs by maximum CTCAE grade (Grade 1, Grade 2, Grade 3, Grade 4, Grade 5)
- any serious TEAEs
- any study drug related serious TEAEs
- any TEAEs leading to death
- any serious TEAEs by maximum CTCAE grade (Grade 1, Grade 2, Grade 3, Grade 4, Grade 5)

The following summary tables will be provided by SOC and PT, by treatment group:

- Incidence of TEAEs
- Incidence of study drug related TEAEs
- Incidence of TEAEs leading to study drug discontinuation.
- Incidence of study drug related TEAEs leading to study drug discontinuation
- Incidence of TEAEs by maximum CTCAE grade (Grade 1, Grade 2, Grade 3, Grade 4, Grade 5)
- Incidence of serious AEs (only if incidence of serious AEs and serious TEAEs differs)
- Incidence of serious TEAEs
- Incidence of study drug related serious TEAEs
- Incidence of serious TEAEs by maximum CTCAE grade (Grade 1, Grade 2, Grade 3, Grade 4, Grade 5)

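### The SAP's fallback for AE intensity still missing after query uses looser triggers for Grades 4 and 5 than the protocol's grade definitions, so a minor or non-fatal AE could be tabulated as life-threatening or fatal

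*SAP*

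**What the plan says.** SAP 10.7.1 covers missing seriousness, intensity and relationship assessments "that have been queried and remain missing, will be treated 'worst case' for presentation filtering purposes as follows". For intensity there are three steps:

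- The first step looks only at vital status: "If subject has died, AE will be regarded Grade 5 intensity".
- The second step applies to survivors and looks at treatment of the event: "If subject has not died but subject had intervention indicated for the AE, AE will be regarded Grade 4 intensity".
- The third step is the default: "If none of the previous conditions are met, AE will be regarded Grade 3 intensity".

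The same section reports "any TEAEs by maximum CTCAE grade" in the overall AE summary and repeats the by-grade layout by system organ class (SOC) and preferred term (PT), for all TEAEs and for serious TEAEs. These layouts list Grades 1 to 5 and have no row for a missing grade. TEAEs leading to death have their own line in the overall summary.

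Protocol 11.2 defines the grades that investigators assign. An event calling for only slight treatment sits at "Grade 2 Moderate; or minimal, local or non-invasive intervention indicated". Grade 4 needs life-threatening consequences or an intervention that is urgent. The top grade is "Grade 5 Death related to AE". Protocol 11.2.3 allows a fatal outcome only where the AE itself resulted in death. Of the remaining AEs it says: "ongoing at the time of death that did not contribute to the subject's death, the outcome should be considered not resolved".

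**The concern.** The SAP's triggers resemble the protocol's grade definitions with the qualifiers removed. Grade 4 loses the requirement of urgency, and Grade 5 loses the link between the AE and the death. An ungraded AE that needed only minimal treatment would therefore be shown as Grade 4. An ungraded AE that resolved before an unrelated death would be shown as Grade 5, although its own recorded outcome says otherwise.

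At stake is how the safety tables read. In a trial of about 80 subjects, Grade 4 and Grade 5 rows are likely to be sparse, so a single entry there draws attention. An entry produced only by imputation would have to be explained, and nothing in the SAP says that it will be marked as imputed.

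**Working it through.** The plan gives no figure to reproduce, so the check is mainly a comparison of texts.

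**Step 1: triggers against definitions.**

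| Grade | SAP 10.7.1 trigger when intensity is missing | Protocol 11.2 definition | What the trigger omits |
|---|---|---|---|
| 5 | the subject died | death related to that AE | the link between AE and death |
| 4 | alive, and an intervention was indicated | life-threatening consequences, or urgent intervention | urgency |
| 3 | everything else | severe or medically significant, or hospitalization indicated, among others | (default grade) |

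An AE needing minimal, local or non-invasive intervention is Grade 2 in the protocol but meets the SAP's Grade 4 trigger. An AE with a recorded outcome of recovered, in a subject who later died of something else, cannot be Grade 5 under Protocol 11.2 or fatal under 11.2.3, but it meets the SAP's Grade 5 trigger.

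**Step 2: does the imputed grade reach a table?** Yes, as written. The by-grade layouts have no missing row, and SAP 10.7.1 says that when an event recurs the worst severity is summarized. An imputed grade can therefore replace a subject's recorded lower grade.

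**Step 3: can the Grade 5 row and the death line disagree?**
- The last dose is on Day 56 at the latest, and treatment emergence ends 28 days after it: 56 + 28 = Day 84 (protocol day numbering).
- AEs are collected to Day 98, which leaves 98 − 84 = 14 days.
- Suppose a subject dies of an AE that began in those 14 days and also has an earlier, resolved TEAE left ungraded after query. The earlier TEAE is tabulated as Grade 5. The line for TEAEs leading to death, if built from recorded outcome, does not count the subject.
- If the fatal AE was itself treatment-emergent, the overall summary agrees, but the table by SOC and PT still shows Grade 5 against an unrelated term.

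**Step 4: size.** With 40 subjects per arm (SAP 6.1.1), one subject moved into a row changes it by 1/40 = 2.5 percentage points. The change is zero if the subject already has a recorded AE of that grade or higher among the events counted for that row: any TEAE for the overall summary, or the same term for a PT row. The documents do not say how many AEs stay ungraded after query. As an assumption for scale only, 0 to 3 subjects in an arm would give 0 to 3/40 = 7.5 points at most.

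**The case against.** The strongest reply is that this is a declared worst-case convention, not a second set of grade definitions. Protocol 11.2 tells investigators how to grade. SAP 10.7.1 acts only when grading was queried and never supplied, and giving an unknown value a high grade is not in itself a contradiction. The same list treats missing seriousness as serious and missing relationship as probably related, and those rules can overstate too. Safety has no formal inference (SAP 10.7), and the primary endpoint is untouched.

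Much of this stands. It limits the reach of the point and keeps it minor. It does not fully answer it, because the rule is not a blanket worst case. It branches on known facts, and in doing so it can override the AE's own recorded outcome. Elsewhere the SAP lets known facts restrain imputation: an AE that began before first dose is not made related to study drug, and Table 9 keeps albumin below 20 g/L at Grade 3 because the value alone does not show life-threatening consequences.

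A reader might infer more than the documents support:

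- **That every treated AE, or every AE in a subject who died, is regraded.** Recorded grades are left alone.
- **That false life-threatening or fatal AEs will appear.** They can appear only if intensity remains missing after query in AEs of these kinds.
- **That deaths or serious AEs are miscounted.** The rule imputes intensity only. It does not alter outcome, seriousness or the classification of AEs leading to death.
- **That the AE page already shows such grades to be impossible.** The eCRF page is not in the documents. A fatal outcome is a defined category (Protocol 11.2.1.1), but life-threatening appears only as a seriousness criterion (11.2.2.3). Protocol 11.2 also keeps severity and seriousness apart, so a non-serious AE is not thereby ruled out of Grade 4.

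**Conclusion.** The point holds as a minor wording defect. For intensity still missing after query, both upper triggers are broader than the protocol's definitions, and the Grade 5 trigger can conflict with the recorded outcome of the same AE. The effect is confined to the by-grade AE tables and their agreement with the line for TEAEs leading to death.

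The most that one affected subject can add to a row is 2.5 points, assuming at least 40 treated subjects in the arm. The number of such subjects is unknown and may be zero. The possible disagreement with the death line also assumes that the line is built from recorded outcome, which the SAP does not state.

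**What to change.** In SAP 10.7.1, replace the three steps for missing intensity with:

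1. Grade 5 only if the recorded outcome of that AE is fatal.
2. Grade 4 only if that AE was life-threatening or needed urgent intervention. Both parts of the protocol definition should be kept, since using life-threatening status alone could under-grade an AE that needed urgent intervention. Confirm which eCRF fields identify these cases.
3. Grade 3 otherwise.

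Flag imputed grades in the AE listing, as SAP 6.2.4 and 6.2.5 already do for imputed questionnaire values.

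The cost is a few lines of text, one changed derivation and a check of the eCRF fields. The downside is a slightly less extreme worst case for ungraded AEs. It remains conservative: an ungraded minor AE that was treated would still be shown as Grade 3.
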